There is low risk to the patient in regards to side effects of erythropoietin. In general, neonatal population studies have not shown to have significant serious side effects. Blood counts will have to be monitored to observe for polycythemia as this would increase the risk for blood viscosity and thrombosis. There are rare instances in the adult literature with development of Pure Red Cell Aplasia, which is not evident in the neonates. There is some discomfort with the injections, however this is of minimal risk. Lab draws will be done as part of a routine basis. The benefits to receiving this medication are that it may decrease the need of transfusions and hospitalizations in the period prior to a more definitive surgery.

2.f Early Withdrawal of Subjects

As this is a voluntary research study, study subjects will be allowed to withdraw from the study before completion at any time. If a withdrawal occurs before initiation of the intervention, the subject will be excluded from the study.

2.g When and How to Withdraw Subjects

A family may wish to withdraw the study subject from the study at any time. When the decision to withdraw is made after discussions with the clinical staff, a member of the research team will be notified. The date, time, and reason of the withdrawal should be noted by the research member and entered into the database. Families will be approached for permission to follow the course of the patient through the proposed study period even if the intervention was stopped.

2.h Data Collection and Follow-up for Withdrawn Subjects

Families will be approached for permission to follow the course of the patient through the proposed study period even if the intervention was stopped. An intention to treat analysis will be applied to the study subject pertaining to the research arm assigned.

2.i Blood transfusion guidelines

Absolute indications:

- Hematocrit <30%

Relative Indications:

- Hematocrit <40% AND one of the following
 - Clinical acidosis
 - Low oxygen saturations (<75%) in room air
 - Requires supplemental oxygen
 - Requires respiratory support (Ventilator, positive pressure)

When a transfusion is needed, a 10 ml/kg aliquot volume should be given.

E3 Study Drug

3.a Description

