Epoetin alfa is a recombinant form of human erythropoietin used to stimulate erythropoiesis. Iron then helps support proper heme formation with the production of hemoglobin. EPO is administered by injections. Iron will be administered orally or intravenously if orals are not tolerated.

3.b Treatment Regimen

Experimental: Epoetin alfa and iron supplements:

Patients in the treatment group will receive weekly erythropoietin injections for 6 weeks starting before 8 weeks of age (at least one week after their surgery) at 500 units/kg/injection (SQ or IV).(Donato 2005 & Maier 2002) Oral ferrous sulfate 3 mg/kg/day of elemental iron will be given throughout the study if enteral feeds are tolerated which is an accepted treatment for anemia and prevention of anemia. If oral iron cannot be tolerated and there is laboratory evidence of iron deficiency, intravenous iron (either Iron sucrose or Iron dextran) will be used to replace iron stores based on the calculated iron deficit: Total replacement dose (mg of iron) = 0.6 x weight (kg) x [100 -

(actual Hgb /Desired Hgb x 100)]. This will be given in 5-7 mg/kg every day until the total replacement dose is achieved.

Iron studies (Serum iron, ferritin, total iron binding capacity) will be obtained at baseline and at week 14 with the final lab draw. If intravenous iron is used for replacement, iron studies will be repeated after replacement to ensure adequate iron stores.

All injections will be administered by a member of the subject's care team (bedside nurse, nurse practitioner, or physician) with a weekly visit in the cardiology clinic or in the hospital if the infant remains hospitalized after being dispensed by the research pharmacist.

A complete blood count will be obtained in the hospital prior to initiation of treatment for baseline measurements and to confirm eligibility if not obtained within 48 hours prior to the 1st injection as a part of the patient's standard of care. It will be repeated weekly (weeks 2-7) whether inpatient or outpatient, to confirm that there is no over-shoot with a hematocrit >45%. Labs will be reviewed prior to treatment. Treatment will be held for hematocrit levels >45%. There will be another lab drawn 14 weeks after the initial injection. Outpatient visits and lab draws will be paid for by the study grant. All labs will be analyzed by the Rady Children's Hospital Laboratory. The study drug will be provided by the study grant.

Observational Control:

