- Age/adjusted age
- Weight
- Oxygen saturation
- Compliance of medication
- Complete blood count
- Transfusions needed
- Hospitalizations
- Adverse events (Severity, expectedness, and relationship)

G Statistical Plan

G1 Sample Size Determination and Power

This will be a randomized controlled single center prospective study of up to 60 patients to account for drop out rate. There will be a minimum 20 treatment patients and 20 control patients enrolled. This sample size is based on a 2 proportion population formula with the assumption that without treatment about 80% of infants need transfusions (based on our experience), and 40% of infants with erythropoietin will need transfusions.

G2 Interim Monitoring and Early Stopping

Unforeseen inaccuracies in design assumptions, in particular having to do with the number of infants who need transfusions without treatment could lead to decreases in the trial's statistical power to detect treatment effects. Accordingly, an analysis will be conducted to estimate the variance of the estimated difference, between the two arms in regards to number of transfusions. This analysis will be conducted within the intention-to-treat framework under which the primary analysis of the primary endpoint will be conducted.

To allow time for corrective action if necessary, this analysis will be performed approximately after 10 patients have been enrolled in both arms. If necessary, this method will be used to obtain a recommended increase in sample size.

An interim analysis of futility will also be performed to determine if the study should continue. This will be done when 10 subjects in each arm have completed the study. The study will be terminated if there is no absolute decrease in number of transfusions per subject.

It is possible that the DSMB may consider it necessary to stop the trial early due to safety concerns. To monitor safety, adverse event rates will be compared between the two trial arms and reported to the DSMB.

In addition, the research team will perform an analysis after the first 5 subjects have completed at least 1 intervention in the EPO arm for safety. These 5 patients will serve as a safety population study.

An interim analysis of safety will be done after 10 patients have enrolled and completed each arm to assess any differences in adverse events between the 2 arms. This will be reviewed by the DSMB who will make the determination as to whether any safety concerns mandate early trial termination.

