G3 Analysis Plan

All primary analyses for efficacy will be performed on an intention-to-treat basis. All subjects will be analyzed according to their group assignment regardless of actual treatment received. In addition, both groups will be compared for safety at the end of the study by comparing adverse events and rates of adverse events. In the safety analysis, subjects will only be included if they actually received treatments in that group. (i.e. if a patient on the EPO arm did not get EPO, they should not be included in the analysis of safety in that arm).

G4 Statistical Methods

All data will only be gathered during the period in which the subjects will be active in the study (from baseline to 14 weeks post initial injection).

For the primary aim, we will compare the number of blood transfusions (one 10 ml/kg aliquot = 1 transfusion) between the two groups with a two-proportion z test. With $n = 20$ subjects per group, this test will have 80% power at the $\alpha = 0.05$ significance level to detect a difference. The primary aim will be assessed when all subjects have completed week 14.

We will compare weight gain and the change in oxygen saturation between baseline measurements and the 6 week follow-up with a two sample t-test. We will also use a linear mixed effects model, with a random intercept included to account for within subject correlation, to determine differences in the longitudinal trends in weight and oxygen saturation between groups. The length of the initial stay will be compared between groups with a two-sample t-test. We will treat the number of re-admissions (in regards to failure to thrive and cyanosis) as a categorical variable, and use Fisher's exact test to determine if there is a difference between EPO and control group readmission counts. We will consider the Mann-Whitney U test as a robust alternative to the two-sample t-test if the assumptions of the t-test are not met by the data.

With a sample size of $n = 20$ subjects per group, the t-tests described above will have 80% power at the $\alpha = 0.05$ level to detect an effect size equal to 0.91 times the common standard deviation. For weight change, assuming that the standard deviation of weights at baseline and the 6 week follow-up equal 1.22 and 1.53 (respectively), and assuming a

moderately high correlation between weight measurements within child of $\rho = 0.70$, this translates to a detectable difference of 1.00 kgs.

G5 Missing Outcome Data

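### The primary z test leaves out baseline hematocrit, a value already scheduled in every infant; a prespecified adjustment would probably gain some power and at worst lose about 1 point

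*Combined protocol and SAP*

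**What the plan says.** G4 names one primary analysis: the number of transfusions is compared "between the two groups with a two-proportion z test". No covariate is mentioned, and no adjusted analysis of the primary endpoint appears elsewhere. G4 adds that with 20 subjects per group "this test will have 80% power at the" 0.05 level. G1 describes its method in one line: "This sample size is based on a 2 proportion population formula". The control rate entered there comes from local practice: "without treatment about 80% of infants need transfusions (based on our experience"). For the other arm, the figure supposed in G1 is that "40% of infants with erythropoietin will need transfusions". E2 2.d and E3 3.c describe 1:1 allocation from a predetermined scheme and mention no stratification by hematocrit.

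On the covariate, E3 3.b states for each arm: "A complete blood count will be obtained in the hospital prior to initiation of treatment for baseline measurements". F2 and Tables 1 and 2 schedule the same test. E2 2.c holds back randomization until hematocrit is below 40%, so every randomized infant has a qualifying value. The transfusion guidelines in E2 2.i use hematocrit in both indications: below 30% on its own, or "Hematocrit <40% AND one of the following" (acidosis, low saturation, supplemental oxygen or respiratory support).

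**The concern.** The primary outcome depends on a guideline built on hematocrit, and E3 3.b requires strict adherence to that guideline. Infants may enter at any hematocrit below 40%, with no lower limit in E2 2.a. If those who enter lower are transfused more often, baseline hematocrit accounts for part of the spread in outcome within each arm. An unadjusted test leaves that spread in the error term. A prespecified adjustment would remove it and would also correct the estimate for any chance difference between arms at entry.

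This matters more than usual because the trial is small and the stated power has little slack. The protocol already sees the issue for another transfusion criterion: C3 wants oxygen saturation compared at baseline so that the arms are alike with respect to the transfusion criteria. Such a comparison reveals an imbalance but does not correct for it.

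**Working it through.** **Inputs from the documents.** Transfusion rates 0.80 (control) and 0.40 (EPO) from G1; 20 per arm, alpha 0.05 and power 80% from G4. Sidedness is not stated; two-sided is assumed.

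**Input not in the documents.** The prognostic strength of baseline hematocrit. It is assumed over a range that starts at zero.

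**1. The plan's own figure.** The unpooled two-proportion formula gives

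n = (1.960 + 0.842)² × (0.8×0.2 + 0.4×0.6) / 0.4² = 19.6, so 20 per arm, with power 80.7%.

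The stated size reproduces. With the pooled z test, 20 per arm gives 75.2% (75.3% by exact enumeration), and 23 per arm would be needed. The unpooled test at this size has an exact type I error of 6.5% at a common rate of 80% and 7.6% at 60%. The pooled test holds 4.8-5.0%. About 75% is therefore the fairer starting point.

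**2. Power with adjustment, latent-normal model.** An underlying risk is the sum of baseline hematocrit and independent noise, and R² is the share due to hematocrit. The adjusted analysis is a linear regression of any transfusion (yes/no) on arm and baseline hematocrit. There were 20,000 trials per setting, 20 per arm, 80% against 40%.

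| Latent R² (assumed) | Pooled z | Adjusted | Change (points) |
|---|---|---|---|
| 0 | 75.7% | 74.7% | -1.0 |
| 0.05 | 75.6% | 76.2% | +0.6 |
| 0.10 | 76.2% | 78.1% | +1.9 |
| 0.20 | 75.4% | 80.1% | +4.7 |
| 0.30 | 75.9% | 82.9% | +7.0 |
| 0.50 | 75.4% | 87.7% | +12.3 |

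**3. A second outcome model.** Here baseline hematocrit is uniform and the outcome logistic, with 20,000 runs. R² is now the share of within-arm variance of the yes/no outcome, so the same association carries a smaller R² than in step 2. Adjusted power was 74.4% at R² 0, 76.9% at 0.05 (odds ratio 1.65 per SD), 79.8% at 0.10, 82.5% at 0.16 and 87.5% at 0.29. The unadjusted pooled test had about 75-76% throughout. Direction and rough size agree with step 2.

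**4. Type I error.** Across the simulation runs, at common rates of 60% and 80%, the adjusted linear model rejected in 4.7-5.7% of trials. A logistic likelihood-ratio test with the same covariate rejected in about 6-6.5%.

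**5. Chance imbalance.** The standard error of the between-arm difference in mean baseline hematocrit is √(2/20) = 0.32 SD, so a gap of at least 0.5 SD arises in about 11% of trials. The average within-arm outcome variance is (0.16 + 0.24)/2 = 0.20, so its SD is 0.447. A gap of 0.5 SD then shifts the observed risk difference by 0.5 × √R² × 0.447. That is about 5, 7 and 9 percentage points at outcome-scale R² of 0.05, 0.10 and 0.16, against a planned difference of 40.

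**6. Larger enrolment.** G1 allows up to 60 infants. At 30 per arm (10,000 runs, model of step 3), adjusted against unadjusted power was 89.8% against 90.0% at R² 0, 91.9% against 90.8% at 0.05, and 94.4% against 90.5% at 0.16. The gain shrinks as the trial grows.

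**The case against.** The strongest reply is that nothing here is wrong. Randomization with an unadjusted test is valid, and its error rate already allows for chance imbalance. The shifts in step 5 are variance, not bias. This stands in full.

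A reader might infer that baseline hematocrit is itself the transfusion trigger, so that an infant entering at 31% must differ greatly in risk from one entering at 39%. The documents do not support this. The guideline applies to the hematocrit when a transfusion is considered, at any time over 14 weeks. Every randomized infant already meets the hematocrit part of the relative indication at entry; what then separates them is a second condition or a fall below 30%. No distribution of baseline hematocrit, and no association with transfusion, is reported.

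There are also reasons to expect a modest predictor. Eligibility truncates the range. Infants who wait until they fall below 40% (E2 2.c) would tend to enter just under it. G5 counts missing outcomes as transfused, which dilutes any association. These arguments stand too, and they are why the range must include values near zero. They do not remove the case for adjustment, because the loss at zero is only about 1 point.

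Finally, G4 applies a test for proportions to a number of transfusions. That question comes first, since the adjusted model depends on its answer.

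**Conclusion.** The point holds as an efficiency improvement. The plan leaves unused a covariate that it already schedules and that is the baseline value of the variable in every transfusion indication. With 20 per arm and a yes/no endpoint, adjustment changes power by between about -1 and +12 points as the assumed latent R² runs from 0 to 0.50. For a weak predictor (R² up to 0.10) the change is about -1 to +2 points. Type I error stays near 5%.

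A reader might conclude that the trial is giving away power at no cost, or that its primary test is flawed. Neither follows: the gain rests on a prognostic strength that the documents do not give, and the z test is valid. The figures also assume rates of 80% and 40%, two-sided alpha and a binary endpoint. The gain for a count endpoint was not computed.

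**What to change.** 1. State in G4 whether the primary endpoint is any transfusion (a proportion) or the number of transfusions (a count).
2. If it is any transfusion, make the primary analysis a covariate-adjusted risk difference: linear regression on arm and baseline hematocrit, entered as a continuous variable. This keeps the risk difference as the quantity estimated. A logistic odds ratio would change that quantity, and its likelihood-ratio test ran slightly above 5% at this size.
3. If it is a count, prespecify a count model with arm and continuous baseline hematocrit, and check its power and type I error first.
4. Define the covariate as the last hematocrit before randomization in both arms. F2 ties the baseline window to the first injection in the EPO arm and to enrolment in the control arm.
5. Keep the unadjusted z test as supportive, and state which form (pooled or unpooled) is used.

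The change should be made before outcome data are seen, including the looks at about 10 per arm in G2. The trial is not blinded, and a covariate chosen later would carry little weight. The cost is SAP wording: no new data and no extra blood draws. The price is about 1 point of power if baseline hematocrit turns out not to be prognostic.

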Informed consent will be obtained by one of the research study members after the initial surgical or catheterization procedure. Each member is well informed of the study objectives, procedures, risks, benefits, physiology of the disease process and mechanism of how the treatment works. The informed consent will be obtained from the patient's parent in a private setting. Details of the study will be presented, and ample time will be given to answer any questions. The parent will have until the eligibility period expires based on the exclusion criteria outlined above to be included in the study. Consent will be obtained in the primary language of the parent. English and Spanish versions of the consent documents will be available and official translators will be used as appropriate. An appropriate official translator will be used during the entire duration of the participant in the study. Informed consent and HIPPA authorization will be documented with the study forms that have been drafted and approved for use in the study and will be kept in a master research file for the duration of the study in a secure area, in a locked drawer by the study team. It will be made clear to the parents that participation in the study is voluntary and that decision to be included or excluded will not compromise the standard of care that the patient deserves. Patients who meet all inclusion criteria except the hematocrit of <40% will be approached and consented, but will not be formally enrolled and randomized into a study group (control or EPO) unless their hematocrit reaches <40% during their eligibility period.

2.d Randomization Method

Study subjects will be randomized 1 to 1 by an algorithm determined by the biostatistician involved. After a study subject has been enrolled into the study, a 2-digit number (1-60) will be assigned. Based on the subject number and predetermined randomization provided, a research pharmacist will dispense the study drug if the subject is enrolled in the intervention arm. This study will not be blinded.

2.e Risks and Benefits

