Screening for eligibility will be done on the Acute Cardiac Unit at Rady Children's Hospital. When an infant with cyanotic congenital heart disease is identified, the patient will be screened for eligibility based on the inclusion and exclusion criteria described above.

F2 Schedule of Measurements

The schedule of measurements is listed in Table 1 and Table 2. For the treatment arm, a physical exam with oxygen saturation will be recorded weekly from baseline and weeks 1-7, 14. A complete blood count will be drawn at baseline (if not already obtained for clinical use, one week post procedure and ≤ 48 hours prior to 1st injection), weekly from weeks 2-7, and at week 14. Iron studies will be drawn at baseline and week 14 unless indicated in between. All labs will be analyzed by the Rady Children's Hospital Clinical Laboratory whether inpatient or outpatient.

The control arm will have a physical exam with oxygen saturations at baseline, week 7 and 14. A complete blood count will be drawn at baseline (if not already obtained for clinical use, one week post procedure and ≤ 48 hours prior enrollment) week 7 and week 14. Iron studies will be drawn at baseline and week 14 unless indicated in between. All labs will be analyzed by the Rady Children's Hospital Clinical Laboratory whether inpatient or outpatient.

F3 Visit 1

Visit 1 will be prior to 8 weeks of age and at least 1 week post procedure while in the hospital. After confirmation of eligibility for the study, a physical exam and oxygen saturation will be obtained, and the 1st dose of the intervention will be given by the subject's care team if in the EPO arm.

F4 Visit 2 etc.

Visit 2-14 may either be obtained in the hospital or in the clinic setting. A physical exam and oxygen saturation will be obtained. A complete blood count will be obtained weekly from weeks 2-7 in the EPO arm. A complete blood count will be obtained in the control group at week 7 or earlier if indicated by the subject's care team. Study injections will be given after the lab has been reviewed and confirmed there is no overshoot (Hct >45%). There will be a final physical exam and labs at week 14 of the study, which will complete the participation of the study.

F5 Safety and Adverse Events

5.a Safety and Compliance Monitoring

Safety and Compliance Monitoring will follow standard principles as outlined below.

5.b Medical Monitoring

i Investigator

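### Oxygen saturation is compared by an unadjusted t-test on change; adjusting for the baseline value already recorded would probably be more precise, by an amount the documents cannot fix

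*Combined protocol and SAP*

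**What the plan says.** Section G4 (Statistical Methods) sets the comparison for weight and oxygen saturation: "We will compare weight gain and the change in oxygen saturation between baseline measurements and the 6 week follow-up with a two sample t-test". It offers the Mann-Whitney U test if the t-test's assumptions fail. It names no baseline covariate.

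G4 then adds a second analysis of the same two outcomes: "We will also use a linear mixed effects model, with a random intercept included to account for within subject correlation". Its purpose is to compare longitudinal trends between arms. The text does not say whether baseline is a covariate, a mean constrained to be equal across arms, or simply the first outcome time point.

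The baseline value exists in both arms. Section F2 has saturation recorded in the EPO arm at baseline, weekly in weeks 1 to 7 and at week 14. For controls: "The control arm will have a physical exam with oxygen saturations at baseline, week 7 and 14".

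On size and power, section G1 says: "There will be a minimum 20 treatment patients and 20 control patients enrolled". For 20 per group, G4 states that "the t-tests described above will have 80% power at the $\alpha = 0.05$ level"; the effect meant is 0.91 SD. It gives SDs of 1.22 and 1.53 and a within-child correlation of 0.70, for weight only.

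**The concern.** A change score subtracts the whole baseline value, which fixes the slope of follow-up on baseline at 1. A model with baseline as a covariate estimates that slope. In a randomised comparison both target the same treatment effect, but the change score carries extra noise whenever the true slope differs from 1.

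The trial is small: the t-tests reach 80% power only for an effect of 0.91 SD. Oxygen saturation is a named secondary outcome (C2). Precision lost on it could leave a real difference undetected when the data to recover that precision are already scheduled.

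**Working it through.** **Inputs.** From the documents: 20 per group (G1, G4), 1:1 allocation (E2, 2.d), alpha 0.05, 80% power at 0.91 SD, and for weight s0 = 1.22, s1 = 1.53, rho = 0.70 (G4). Assumed: a two-sided test, and every SD and correlation for saturation, since none is given.

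**The plan's own figures.** Noncentral t with 38 df gives 80.1% power at 0.91 SD. The SD of weight change is sqrt(1.22² + 1.53² − 2 × 0.70 × 1.22 × 1.53) = sqrt(1.2161) = 1.103, and 0.91 × 1.103 = 1.003 kg, against the stated 1.00 kg. Both reproduce.

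**Formulas**, per child, with s0 and s1 the baseline and follow-up SDs:

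- Change score: s0² + s1² − 2·rho·s0·s1
- Baseline-adjusted: s1²(1 − rho²)
- Difference: (s0 − rho·s1)², which is never negative and is zero only when the slope rho·s1/s0 equals 1
- With equal SDs, the ratio of adjusted to change-score variance is (1 + rho)/2, so the reduction is (1 − rho)/2
- Estimating the slope with N = 40 multiplies the adjusted variance by 1 + 1/(N − 4) = 1 + 1/36 = 1.028

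**Saturation, equal SDs assumed.** Net reduction is 1 − 1.028 × (1 + rho)/2. Power is at a true difference of 0.91 SD of change, where the change-score test has 80%; the adjusted model uses 37 df.

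| rho | Large-sample reduction | Net at 20 per arm | Power, adjusted model |
|---|---|---|---|
| 0.3 | 35% | 33% | 93% |
| 0.5 | 25% | 23% | 89% |
| 0.7 | 15% | 13% | 85% |
| 0.9 | 5% | 2.4% | 81% |

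Simulation (40,000 trials of 20 per arm) gave net reductions of 33.5%, 23.4%, 13.0% and 2.5%.

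**Saturation, unequal SDs assumed** (large-sample reduction):

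| Follow-up SD / baseline SD | rho 0.3 | rho 0.5 | rho 0.7 | rho 0.8 |
|---|---|---|---|---|
| 0.8 | 50% | 43% | 37% | 36% |
| 1.25 | 22% | 11% | 2% | 0% |

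The zero arises because 0.8 × 1.25 = 1, so the slope is exactly 1.

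**Chance imbalance, one example.** With equal SDs and rho 0.5, the SD of change equals the SD of a single value. One standard error of the baseline difference between arms is sqrt(2/20) = 0.316 SD. A baseline imbalance of that size shifts the change-score contrast by (1 − 0.5) × 0.316 = 0.158 SD, which is 17% of the 0.91 SD detectable effect. This is the same loss as in the first table, not an extra one: 0.158² = 0.025, and 0.025/0.100 = 25%.

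**Weight, the plan's inputs.** The slope is 0.70 × 1.53/1.22 = 0.88. The adjusted variance is 1.53² × (1 − 0.49) = 1.1939, and 1.1939/1.2161 = 0.982, a reduction of 1.8%. Net of slope estimation, 1.028 × 0.982 = 1.009, a loss of about 1% (simulation: 1.2%).

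**The case against.** The strongest reply is that the planned test is sound and the size of the gain is unknown. Allocation is random: "Study subjects will be randomized 1 to 1 by an algorithm determined by the biostatistician involved". A reader might infer that regression to the mean biases the change-score comparison. It does not: regression to the mean is equal across arms in expectation, and only chance imbalance, which is variance, remains. This part of the objection stands.

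A reader might also take one range, such as 13% to 33%, as a property of this trial. The documents do not support that. They give no SD or correlation for saturation, and borrowing all of the weight inputs would make the gain vanish. Whether mean saturation drifts over time does not help, because the gain depends on the SD ratio and the correlation. Nor is adjustment quite free at this sample size.

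It may be said that the mixed model already does the work. It might, but G4 does not settle it. If each arm has its own free baseline mean, the model's contrast for change is essentially the change-score contrast. It matches the adjusted analysis only if baseline is a covariate or the baseline means are constrained to be equal. The t-test is also the only saturation analysis with a power statement.

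Two further extensions fail. Replacing the weight test buys nothing on the plan's own inputs and would detach that analysis from its 1.00 kg figure. And adjustment does not meet the wish in C3 to see whether the arms start alike; it only makes the comparison less sensitive if they do not.

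**Conclusion.** The point holds as a minor efficiency recommendation for one secondary outcome. The direction is secure: in large samples the adjusted variance is never larger, and at 20 per arm the most that can be lost is about 2.8%. The size is not secure. It is about 13% to 33% net if the SDs are equal and rho lies between 0.3 and 0.7. Across rho 0.3 to 0.9 and SD ratios 0.8 to 1.25, the large-sample gain runs from about nil to 50%. The documents cannot narrow this.

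The planned test is not wrong or biased. The primary analysis and the sample size are unaffected.

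**What to change.** In G4, for oxygen saturation, replace the two-sample t-test on change with a linear model of the follow-up value, with arm and baseline saturation as covariates. For the mixed model, state that the baseline means are constrained to be equal across arms or that baseline enters as a covariate. Leave the weight analysis as it is.

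The cost is SAP wording, settled before the data are compared by arm. No new measurement is needed. The statistical price is one degree of freedom: about 2.8% of variance at 40 infants, or 1/56 = 1.8% if all 60 are analysed.
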